5.7.2. Recording, Evaluating, and Assessment of AEs/SAEs

The method of recording, evaluating, and assessing causality and relationship to study drug of AE and SAE and the procedures for completing and transmitting SAE reports are provided in **Appendix 2** of the Master Protocol (**LDOS-21-001**). Care will be taken not to introduce bias

when detecting AEs and/or SAEs. Open-ended and non-leading screen prompts is the preferred method to inquire about AE occurrences.

5.7.3. Follow-up of AEs and SAEs

After the initial AE/SAE report, the Investigator is required to proactively follow each participant at subsequent contacts. All Seawall be followed until resolution, stabilization, the event is otherwise explained, or the participant is lost to follow-up (as defined in Section 4.3). Further information on follow-up procedures is given in **Appendix 2** of the Master Protocol (**LDOS-21-001**).

5.7.4. Regulatory Reporting Requirements for SAEs

- Prompt notification by the Investigator to the Sponsor of an SAE is essential so that legal obligations and ethical responsibilities towards the safety of participants and the safety of a study intervention under clinical investigation are met.
- The Sponsor has a legal responsibility to notify the FDA authority about the safety of a study intervention under clinical investigation. The Sponsor will comply with specific regulatory requirements relating to safety reporting to the regulatory authority (for example, the filing of a Form 3500A and/or Annual Safety Report under the applicable IND), Institutional Review Boards (IRBs) and Investigators.
- Investigator safety reports must be prepared for suspected unexpected serious adverse reactions (SUSARs) according to applicable regulatory requirements and Sponsor policy, and forwarded to Investigators, as necessary.
- An Investigator who receives an investigator safety report describing a SAE or other specific safety information (e.g., summary or listing of SAEs) from the Sponsor will review and then file it along with the Investigator's Brochure and will notify the IRB, if appropriate according to local requirements.

5.7.5. Pregnancy

- Details of all pregnancies in female participants and female partners of male participants will be collected after the start of study intervention and until the end of the follow-up period.
- If a pregnancy is reported, the Investigator should inform the Sponsor within 24 hours of learning of the pregnancy and should follow the procedures outlined in **Appendix 4** of the Master Protocol (LDOS-21-001).
- Abnormal pregnancy outcomes (e.g., spontaneous abortion, fetal death, stillbirth, congenital anomalies, and ectopic pregnancy) are considered SAEs.

5.7.6. Disease-Related Events and/or Disease-Related Outcomes Not Qualifying as AEs or SAEs

Disease-related events (DREs) are addressed Section 6.2.6 in the Master Protocol (LDOS-21-001).

5.8. Treatment of Overdose

Recommendations with regard to treatment of overdose are provided in Section 6.3 of the Master Protocol (LDOS-21-001)

5.9. Pharmacokinetics/Pharmacodynamics

Pharmacokinetic and pharmacodynamic parameters are not evaluated in this study.

6. **EXPLORATORY ENDPOINTS**

6.1. Exploratory Endpoints: Tracking participants' self-assessments on multiple dimensions.

Patient Recorded Outcomes (PRO) for symptom severity: Participants will select personally relevant COVID-19 symptoms from a list and track the severity of each on a daily basis before and after start of treatment using an 11–point NRS ranging from "None" to "Extreme". After 15 days, participants will continue to complete brief daily and weekly diaries for a total of 3 months following first day of treatment. The list of symptoms will initially contain typical COVID-19 symptoms but will enable participants to add other symptoms that emerge that they attribute to their illness.

Endpoints: The presence, severity and duration of COVID-19 signs and symptoms. Specific metrics include assessing the slope, time course, and extent of change in the mean severity score of various subsets of endorsed symptoms from prior to onset of treatment to specified post-treatment days (e.g., Days 3, 7, 11, 15) and to specified clinical milestones (e.g., sustained clinical recovery).

Hypotheses: The patient population consists of recently PCR-tested individuals who have begun to show one or more cardinal symptoms of COVID-19. Based on published epidemiological surveys the symptoms experienced by outpatients will typically persist over about 4–8 days, with some participants showing an initial period of symptom escalation, and another subset experiencing deterioration of their clinical status around day 7–15, potentially requiring hospitalization. Moreover, a significant minority of participants will report some degree of enduring symptoms over the course of the ensuing weeks to months. We hypothesize that the daily trend following treatment will differ between the treatment groups and the placebo group with a faster and steeper decline in symptom severity scores after treatment and with significantly greater proportional improvement across symptoms with treatment than with placebo. We hypothesize that any early trend towards increasing severity will invert sooner following treatment for key symptoms pertaining to everyday performance (difficulty breathing, myalgia and fatigue) will differ significantly and by more than 50% between treatment and placebo groups.

Purpose: To demonstrate the utility of participants' self-assessed symptom severity ratings to measure the degree and time course of clinical improvement and differentiate between treatment and controls groups.

PRO for impact of illness on performance: Participants will respond daily to three functional queries, on an 11–point NRS ranging from "No Limitations" to "Extreme Limitations", tracked daily before and after start of treatment. The three discrete dimensions of impact of treatment on capability to perform are: impaired ability to perform my essential tasks and duties; impaired ability to care for myself without assistance, and impaired ability to assist others.

Endpoints: The presence, extent and duration of COVID-19-related functional impairments. Specific metrics include assessing the slope, time course, and extent of change in the three impairment scores from prior to onset of treatment to specified post-treatment days (e.g., Days 3, 7, 11, 15) and to specified clinical milestones (e.g., sustained clinical recovery).

Hypotheses: We hypothesize that the daily trend following treatment will differ between the treatment and placebo groups with a quicker and steeper decline in functional impairment scores with significantly greater proportional improvement with treatment v. placebo (the treatment group will improve faster than the control group). We hypothesize that any existing trend towards increasing functional impairment will invert earlier following treatment than with placebo. We hypothesize that the 7–day AUC of functional impairment scores post treatment will differ significantly and by more than 50% between treatment and placebo groups.

Purpose: To demonstrate the utility of participants' self-assessed impairment ratings in capturing the degree and time course of improved real-world performance and differentiate between treatment and control groups.

6.2. Participant Protocol Debrief: Participants will respond to a trio of probes.

 Participants will generate retrospective assessments of their overall degree of improvement at Day 15 following onset of treatment and at termination of participation using the PGIC (Patient's Global Impression of Change) scale, an established, widelyused 7-point qualitative rating scale of perceived treatment efficacy ("very much improved," "much improved," "minimally improved," "no change," "minimally worse," "much worse," or "very much worse.").

Endpoint: The perceived presence or absence of overall clinical improvement.

Hypothesis: The treatment groups will score higher on the PGIC than the placebo group.

2. Participants will respond to the following prompt at the conclusion of their participation: "I believe I received: 1) an investigational drug, or 2) a placebo".

Endpoint: Effectiveness of blinding provisions.

Hypothesis: At least 20% of participants will not correctly select treatment.

Purpose: to explore the degree of awareness/ perception of participants to the impact of treatment.

3. Participants will be given the option of selecting a short narrative that best describes their own individual outcome from a pool of alternatives ("sum-ups"), as well as the option of composing an open-ended narrative account.

Endpoints: Qualitative information/insights extracted from participant's accounts describing the personal significance of their treatment experience.

Hypothesis: Participant descriptions of disease and treatment will reveal the patient point of view on efficacy and aspects of the treatment that matter to them.

Purpose: In accordance with FDA's PFDD principles, to learn what aspects of disease and treatment matter most to patients.

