Exploratory endpoints will be evaluated for all study participants. The rate of hospitalization and all-cause mortality rate will be assessed for all participants. Additionally, multiple PRO endpoints will be used to establish how participants feel and function in relation to disease and treatment. These endpoints will include daily ratings of symptom type and severity from which estimates of symptom onset and duration can be derived, along with the tracking of dynamic trends over time. Symptoms will be captured using an 11-point numerical rating scale (NRS) ranging from "None" to "Extreme", which corresponds to 0-10. The default symptom list provided to participants will include labels for 20 symptoms that have been commonly associated with COVID-19 (see Appendix 3 in the Master Protocol, LDOS-21-001) with the capability of adding individualized symptoms not appearing in the common list. Daily ratings of perceived incapacity will also be obtained to assess the overall impact of symptoms on participant's day-today functionality, using the 11-point NRS with a range from "No Limitation" to "Extreme Limitation." At the conclusion of their participation, participants will also report on their global impression of therapeutic change using an established 7-point scale (PGIC), their belief regarding active v. placebo group assignment, and their qualitative impressions of their illness experience elicited through narrative probes. Participants will be oriented to and trained on the use of these PRO instruments to ensure comprehensibility and usability, in accordance with recent FDA guidance for assessing COVID-19 in outpatient clinical trials. In addition to the above subjective measures, daily spO2 and body temperature ratings will be captured using Sponsor-provided pulse oximeter and thermometer, and recorded by participants.

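### Extent of change measured up to a participant's own recovery is nearly blind to faster recovery if recovery means low scores, and exists only for those who recover (exploratory endpoints, Section 6.1)

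*Protocol*

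**What the plan says.** Section 6.1 has two endpoint paragraphs of the same form. For symptoms: "Specific metrics include assessing the slope, time course, and extent of change in the mean severity score of various subsets of endorsed symptoms". For function: "Specific metrics include assessing the slope, time course, and extent of change in the three impairment scores from prior to onset of treatment". Both run from before treatment "to specified post-treatment days (e.g., Days 3, 7, 11, 15) and to specified clinical milestones (e.g., sustained clinical recovery"). Ratings are on a 0–10 scale with 0 as no symptom or no limitation (Section 1.4.2).

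The symptom hypothesis is a "faster and steeper decline in symptom severity scores after treatment and with significantly greater proportional improvement across symptoms with treatment than with placebo". For function, one hypothesis is that the 7-day "AUC of functional impairment scores post treatment will differ significantly and by more than 50% between treatment and placebo groups".

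On the course of illness, Section 6.1 states that "the symptoms experienced by outpatients will typically persist over about 4–8 days". It also expects one subset to worsen in the second week, possibly to the point of admission, and a sizeable minority to have symptoms for weeks or months.

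Section 7.4.2 treats all these endpoints as exploratory, analyses them in the Full Analysis set (FAS), and already names Kaplan-Meier and log-rank methods for cumulative incidences. Sustained clinical recovery is not defined in this protocol. It appears only as an example, once in each endpoint paragraph.

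**The concern.** The purpose stated in Section 6.1 is to measure the degree and time course of improvement and to separate the arms. A change score does that when both arms are read at the same time. When each participant is read at the moment of recovery, the endpoint of the measurement is set by the outcome itself. If recovery means low scores, everyone who gets there has moved from baseline to about the same low value, whether it took four days or fourteen. A benefit in speed then leaves no trace in this metric.

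The second problem does not depend on how recovery is defined. A participant who never recovers has no value for change to recovery or slope to recovery. If treatment alters who recovers, the groups compared are no longer the randomised ones.

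At stake is the reading of one named exploratory metric, which could show no difference alongside other metrics that do.

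**Working it through.** **Plan's own figure.** Section 6.1 states none for these metrics. The trial's design figure is 659 per group. For 6% against 2.4%, with a two-sided 5% test, pooled variance, no continuity correction and 90% power, the formula gives 651 per group, and 659 gives 90.4% power. The figure reproduces to within 8 participants. It is used below only as the arm size.

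**Structure of the metric.** Let Y0 be the baseline score, T the day of recovery and c the low score that defines recovery (an assumption, since the protocol gives no definition).

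- Extent to recovery: E = Y0 − Y(T) ≈ Y0 − c. T has dropped out.
- Slope to recovery: S = (Y0 − c)/T. T remains.
- Change to a fixed day d: Y0 − Y(d). This depends on speed unless both arms are already at the floor.

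An example with Y0 = 5, c = 0 and linear decline, recovering on day 6 in one arm and day 5 in the other:

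| Metric | T = 6 | T = 5 |
|---|---|---|
| Extent to recovery | 5 − 0 = 5 | 5 − 0 = 5 |
| Slope to recovery | 5/6 = 0.83 | 5/5 = 1.00 |
| Change to Day 3 | 5 × 3/6 = 2.5 | 5 × 3/5 = 3.0 |

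**Simulation 1, exponential decay.** All inputs are assumed: 659 per arm, 400 trials per setting, baseline mean 5 (SD 1.8), and recovery on the first of two consecutive days at or below a threshold of 0.5, 1 or 2. Decay on active is 15% or 30% faster. Time to recovery was compared by a rank test, with non-recoverers set to Day 30. Rejection rates at 5%, as ranges over the three thresholds:

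| Metric | 15% faster | 30% faster |
|---|---|---|
| Extent to recovery | 4–8% | 4–8% |
| Slope to recovery | 96–98% | 100% |
| Time to recovery | 87–99% | 100% |
| Change to Day 7 | 43–50% | 91–94% |

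With no treatment effect, extent rejected in 4.5–6%. The mean difference in extent under the 30% effect was 0.02–0.04 points on the 0–10 scale. With 400 trials, the simulation error at 5% is √(0.05 × 0.95/400) = 1.1 percentage points, so 4–8% is close to the null rate.

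**Simulation 2, linear decline.** Assumed: baseline 5 (SD 1.5), recovery at 6 against 5 days (SD 2), 659 per arm, 1,000 trials. Extent to recovery rejected in 5%. Slope to recovery, time to recovery, change to Day 3 and 7-day AUC each rejected in about 100%. Change to Day 7 rejected in 29%, and changes to Days 11 and 15 in 5% each.

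**Do Days 11 and 15 really fail?** Simulation 2 lets nearly everyone recover in five or six days, which leaves out the slow recoverers that Section 6.1 describes. Adding them (assumed mean 25 days on placebo, about 21 on active) gives:

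| Slow recoverers, placebo / active | Day 11 | Day 15 |
|---|---|---|
| 20% / 20% | 20% | 26% |
| 20% / 15% | 60% | 50% |
| 30% / 20% | 98% | 93% |

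The floor at the later fixed days is therefore a product of the simpler model.

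**Selection.** In simulation 1 about 98–100% of participants recovered, so its figures show insensitivity and do not measure selection bias. The selection argument is structural: E and S have no value for a participant without a recovery date.

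**The case against.** The strongest reply is that recovery is undefined here and may be defined in the Master Protocol or the SAP, neither of which is at hand. A reader might infer that scores are near zero at recovery by definition and that the metric cannot detect an effect. The protocol supports neither statement. Both assume a score-based definition. If recovery is defined on symptoms alone, or by a criterion other than these scores, the three impairment scores need not be low at that point, and nor need every symptom subset. This stands, and it is why the insensitivity is stated as conditional. It does not remove the selection problem.

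It is also fair that the sentence names three metrics. Time course to recovery can cover how long recovery takes, and duration is already a listed endpoint. A reader might conclude that slope to recovery should be deleted too. Slope detects the effect in 96–100% of simulated trials, so its weakness is only that it is conditional on recovery.

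A further tempting step is to demote Days 11 and 15 because symptoms typically last 4–8 days. Those days cover the late worsening and lasting symptoms that the same section expects, and the figures with slow recoverers show that they can separate the arms.

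Finally, a reader might fear that a real benefit would go unseen. No stated hypothesis rests on extent of change at recovery, and Day 3, Day 7, slope and the 7-day AUC would still show it.

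**Conclusion.** The point holds in a limited form and is minor. Given a low-score definition of recovery, extent of change to that milestone is nearly uninformative about treatment: it rejects in about 4–8% of trials, against 87–100% for time to recovery. Two models with different assumed shapes agree, and the algebra shows why. The percentages rest on assumed baseline scores, recovery speeds and thresholds; the cancellation of T rests only on the low-score definition. Whatever the definition, extent and slope to recovery compare only those who recovered. The milestone is an example within exploratory endpoints, so neither the primary nor the secondary conclusions change.

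**What to change.** In both endpoint paragraphs of Section 6.1:

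- Limit extent of change to the fixed days, keeping Days 3, 7, 11 and 15.
- Define sustained clinical recovery, or point to where it is defined.
- Analyse it as time from Day 1 to sustained recovery in the whole FAS, by the Kaplan-Meier and log-rank methods of Section 7.4.2. Keep hospitalised or deceased participants in as not recovered, so that a death is not censored at its date as if recovery were still possible.
- If slope to recovery is kept, label it as conditional on recovery.

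The cost is wording in Section 6.1 and matching text in the SAP. No new data are needed, because daily ratings through Day 90 are already scheduled.

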Statistical Methods: The study will aim to enroll up to 1465 participants, which assumes a 10% screen failure rate, with a final allocation of 659 participants in the treatment arm and 659 in the control arm.

This sample size of ensures a power of 90% at a 2-sided α of 5%, assuming a 1:1 randomization, a placebo rate of 6% (of participants with at least one COVID-19–related medically attended contact, due to increased symptom severity, or incidence of death due to COVID-19 through Day 30) and an assumed relative risk reduction of 65% to 2.4% in the active treatment arms. The statistical test of the null hypothesis of no between-group difference in proportions, as specified

in the primary endpoint, will be tested using a χ^2 test at a two-sided 5% significance level. An interim analysis for futility will be performed after 50% of participants have completed the primary endpoint assessment at day 30. Safety analyses will be performed on the Safety Population, consisting of all participants who are randomized and received study drug, analyzed by actual treatment arm. A more detailed description of the statistical methods can be found in Section 7.

Protocol Title: A virtual Phase 2 randomized, placebo-controlled, double-blind study to evaluate the safety and efficacy of the combination of famotidine and celecoxib as a post-exposure prophylaxis (PEP) for newly-infected COVID-19 patients.

Short Title: LEAP-CT as a post-exposure prophylaxis for newly-infected COVID-19 patients.

Rationale: Please refer to the Master Protocol LDOS-21-001 for a comprehensive background and rationale for this study of a combination of famotidine and celecoxib as post-exposure prophylaxis (PEP) for newly-infected COVID-19 patients.

Overall Design: This is a Phase 2, randomized double-blind placebo-controlled decentralized virtual study in which outpatient participants, newly diagnosed for COVID-19, will be randomized in a 1:1 ratio to one of two study groups (1 treatment group and 1 control group). The study is designed as a virtual trial in that it will be conducted, *in situ*, with home-based participants entering self-assessments via a web-enabled adaptive platform – The participants will be under the oversight of regionally based investigators who will be responsible for study conduct and the review of blinded data on a periodic basis.

Intervention Groups and Duration: The treatment regimen for this study is shown in Table 4.

Regimen	Dose	# of Participants

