7.2. Sample Size Determination

The sample size was estimated assuming that an interim analysis with stopping criteria for futility will be performed after 50% of participants have a primary endpoint assessment at Day 30. The O'Brien-Fleming beta-spending function is used to determine the non-binding futility boundary.

A total of 1318 evaluable participants, defined as part of the Full Analysis population (659 per group) are required to detect a relative reduction in the primary efficacy parameter of 60% in the active treatment arms compared to placebo (from of 6% in the placebo group to 2.4% in the active groups) with 90.0% power and using a two-sided χ^2 -test with 0.5% significance level, assuming variances are pooled, and that continuity correction was not used. Assuming a 10% screen failure rate, 1465 enrolled participants will be required.

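### The exploratory blinding hypothesis (at least 20% wrong answers) excludes only severe unblinding, because answers unrelated to arm would give about 50% wrong

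*Protocol*

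**What the plan says.** Section 6.2 (Participant Protocol Debrief), item 2, sets out the blinding check.

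- Timing: "Participants will respond to the following prompt at the conclusion of their participation".
- Prompt, with two options and no option for not knowing: "I believe I received: 1) an investigational drug, or 2) a placebo".
- Endpoint line: "Endpoint: Effectiveness of blinding provisions".
- Hypothesis line: "At least 20% of participants will not correctly select treatment".
- Purpose line: it speaks of exploring participants' awareness or perception of the impact of treatment.

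The protocol gives no rationale for 20%, no chance value to set it against, and no criterion by arm.

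Other relevant places:

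- The synopsis (section 1.1, Overall Design) has participants "randomized in a 1:1 ratio to one of two study groups (1 treatment group and 1 control group".
- Table 3 lists the belief about assignment among the exploratory efficacy endpoints.
- Section 7.4.2 says such endpoints will be analysed in an exploratory way, with descriptive statistics and exploratory confidence intervals and p-values.

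**The concern.** The endpoint line says the item measures how well blinding worked, and the only yardstick given is a minimum of 20% wrong answers. On a two-option question with equal arms, the natural reference is what participants would score if their answers carried no information about their arm, and that is about 50% wrong. A floor of 20% is far from it. A trial in which a large share of participants knew their arm would still agree with the stated hypothesis.

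What is at stake is interpretation. Section 6 relies on self-ratings of symptom severity, functional impairment and global change. Section 6.1 hypothesises that "functional impairment scores post treatment will differ significantly and by more than 50% between treatment and placebo groups", and section 6.2 that "The treatment groups will score higher on the PGIC than the placebo group". Anyone reading those results will want to know how far participants were aware of their arm, and a statement that the blinding hypothesis was met would tell them little.

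**Working it through.** **Inputs.** The threshold (20% not correct), the two-option prompt and its timing come from section 6.2. The 1:1 allocation to two arms comes from section 1.1. For the number answering, which the protocol does not state, I use the evaluable number in section 7.2 as an assumption: "A total of 1318 evaluable participants, defined as part of the Full Analysis population (659 per group". I repeat the calculation with half that number. The denominator is taken as those who answer. The protocol does not derive the 20%, so there is no figure of its own to reproduce.

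**Step 1: chance value.** Let r be the share of responders in the drug arm and L the share answering drug, equal in both arms because answers are unrelated to arm.

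Share wrong = r(1 − L) + (1 − r)L.

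- r = 0.50: 0.5(1 − L) + 0.5L = 0.50 for any L.
- r = 0.45 or 0.55 (assumption), L = 0.8: 0.53 or 0.47. Even at L = 1 it is 0.55 or 0.45.
- Sampling range at 1318: 50% ± 1.96 × √(0.25/1318) = 50% ± 2.7 points, or 47.3% to 52.7%.
- Distance of 20% from chance: (0.20 − 0.50)/√(0.25/1318) = −21.8 standard errors.

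**Step 2: what 20% wrong means.** Suppose a share k truly know their arm and the rest guess 50/50. Then the share wrong is (1 − k)/2.

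- 20% wrong (80% correct): k = 1 − 2 × 0.20 = 0.60.
- 25% wrong (75% correct): k = 0.50.
- 17% wrong (83% correct): k = 0.66.

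**Step 3: chance that the hypothesis is met.** Exact binomial probability that at least 20% are wrong (at least 264 of 1318, or at least 132 of 659):

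| True % correct | 1318 respondents | 659 respondents |
|---|---|---|
| 75 | above 0.999 | 0.999 |
| 78 | 0.96 | 0.90 |
| 80 | 0.50 | 0.51 |
| 82 | 0.03 | 0.10 |
| 83 | 0.002 | 0.02 |
| 85 | below 0.001 | below 0.001 |

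**Step 4: pooling the arms.** If one arm is fully unblinded and the other guesses 50/50, the share wrong is 0.5 × the guessing arm's share of responders.

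- 50:50 split: 0.5 × 0.50 = 25% wrong. The chance of at least 264 wrong among 659 guessers is above 0.999.
- 45:55 split: 22.5% to 27.5% wrong. In the lowest case (593 guessers), the chance of at least 264 wrong is about 0.997.

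The hypothesis is met in each case.

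**Step 5: which comparison works.** If answers are unrelated to arm, the proportion correct is L in the drug arm and 1 − L in the placebo arm. The two sum to 100% whatever L is and whatever the response rate in each arm. Each arm on its own need not be near 50%: with L = 0.8 and intact blinding, they are 80% and 20%. The excess of the sum over 100% equals the difference between arms in the proportion answering drug. With 659 per arm and half answering drug in each, the 95% half-width of that difference is 1.96 × √(0.25/659 + 0.25/659) = 5.4 points. For one arm's proportion correct it is 1.96 × √(0.25/659) = 3.8 points.

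**The case against.** Four points can be made for the plan.

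1. **The purpose line is wider than blinding.** It speaks of perceived impact of treatment. If the drug works as the other section 6 hypotheses predict, participants may infer their arm from how they fared, so fewer than 50% wrong is expected even with intact blinding. This stands as an explanation for a figure below 50%. It does not justify 20%, and the endpoint line still says blinding.

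2. **The 20% is a prediction, not a pass mark.** No test, decision or statement that blinding will be judged effective is attached. This stands and is why the point is minor. A reader might infer that the sponsor will declare blinding successful on this criterion, but the protocol nowhere says so.

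3. **Estimation is already planned.** Section 7.4.2 promises descriptive statistics and exploratory confidence intervals, and the SAP may add results by arm or a blinding index. This stands too. What remains is the hypothesis sentence itself, which is fixed in the protocol.

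4. **The criterion is not empty.** A reader might infer that it fails only when unblinding is nearly complete. The figures do not support that. At 83% correct, about 66% truly know their arm under the know-or-guess model, and with 1318 respondents the hypothesis is met with probability only 0.002. Severe is the right word.

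**Conclusion.** The point holds as a minor one. The single stated hypothesis on blinding cannot separate intact blinding from substantial unblinding. It excludes severe unblinding, above 80% correct or roughly 60% truly knowing their arm, and little short of that. It can also be met with one whole arm unblinded.

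The 50% benchmark assumes similar response in the two arms, but a 45:55 split moves it by only a few points. The probabilities assume 1318 or 659 respondents. The translation to 60% knowing assumes that the remainder guess at random.

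Two stronger readings should be resisted. A reader might infer that blinding in this trial is inadequate; nothing here shows that, and the blinding procedures sit in the Master Protocol, which section 3.6 refers to and which is not at hand. A reader might also infer that the primary result is compromised; the item is exploratory and does not enter the primary test or the sample size.

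**What to change.** In section 6.2, replace the 20% hypothesis with text such as:

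*The proportion correctly naming the assigned arm will be estimated in each arm with a 95% CI. The two arms will be read together: the sum of the two proportions correct will be compared with 100% (equivalently, the difference between arms in the proportion answering that they received the investigational drug will be compared with 0, with a 95% CI), because a shared leaning to one answer moves each arm away from 50% without unblinding. As the question is asked at the end of participation, a result above chance may reflect perceived efficacy and does not by itself show that blinding failed.*

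The two-arm reading belongs in the protocol text itself. Comparing each arm separately with 50% would make an intact blind look broken whenever most participants lean to one answer. The change cannot remove the ambiguity that comes from asking at the end, so the last sentence states it.

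The cost is a few sentences. The analysis needs only the answer and the assigned arm, both already collected, with no new contact. The downside is that the blinding result may look less favourable than under the 20% floor.
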